##### Dichotomous variables:

- The proportion of responders defined as subjects who achieve both clinical and histologic response (Weeks 16 and 48):
  - Clinical response is defined as the proportion of subjects achieve  $< 4/15$  in all Symptoms of Interest (Gastric Pain Symptoms domain, Stomach Heaviness Symptoms domain, and Diarrhea Symptoms domain) of the Izumo Scale
  - Histologic response is defined as a  $> 75\%$  reduction of peak gastric and/or duodenal eos count from baseline

- The proportion of subjects achieving eosinophilic histologic response defined as a > 75% reduction of peak gastric and/or duodenal eos count from baseline (Weeks 16 and 48)
- The proportion of subjects who achieve < 4/15 in all Symptoms of Interest (Gastric Pain Symptoms domain, Stomach Heaviness Symptoms domain, and Diarrhea Symptoms domain) of the Izumo Scale (Weeks 14 to 16, 30 to 32, and 46 to 48)
- The proportion of subjects for whom the dose of concomitant steroids is reduced to zero (Weeks 24, 32, 40, and 48)

The analysis of the response endpoint will be conducted on the ITT population using the Cochran-Mantel-Haenszel (CMH) test stratified by concomitant corticosteroid treatment at baseline (yes or no). In case the Mantel-Fleiss criterion is not met, the Fisher's exact test will be performed instead of the CMH test. For treatment comparison between a CC-93538 dose and placebo, the 2-sided 95% stratified Newcombe CI ([Yan, 2010](#)) for the difference in proportions using the CMH weights will be provided. Missing data and any observed data after rescue therapy/prohibited medication which may impact the efficacy assessment will be set as non-responders.

Time to event data:

- The time to event of EGE flare (Through Week 48)
- The time to event of use of rescue therapy (Through Week 48)
- The time until concomitant corticosteroid use to zero (From Week 16 through Week 48)

For the time-to-event endpoints, the numbers of subjects who have an event will be summarized. The Kaplan-Meier (KM) estimates of the 25th, median, and 75th percentile of the time to the first event and the 2-sided 95% CIs will be provided. The cumulative number of events, the number of subjects at risk, and the KM estimate of the event rate (i.e., failure probability instead of survival probability) and SE will be provided by time point. The KM plot of failure curves (instead of survival curves) with the number of subjects at risk at each time point will be presented. To test the KM curve in the treatment group is different from that in the placebo group in at least one stratum, a stratified log-rank test will be conducted.

Multiplicity Adjustment

Only one formal statistical test will be performed for the primary endpoint. For any other comparisons, nominal p-value (without adjustment for multiplicity) will be provided as a measure of the strength of association between the endpoint and the treatment effect rather than a formal statistical test. Therefore, the multiplicity adjustment is not applicable in this study.

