### **3.1.2      Induction Phase**

Following a 4-week Screening Period, subjects meeting all inclusion criteria and none of the exclusion criteria will be eligible for enrollment in the Induction Phase. Approximately 45 subjects 12 to 75 years of age, inclusive, with a diagnosis of EGE and with symptoms of EGE will be randomized 2:1 to receive CC-93538 360 mg SC once weekly (N = approximately 30) or matching placebo (N = approximately 15), in a double-blind fashion for 16 weeks. Subjects will be required to have weekly symptom scores of  $\geq 4/15$  for any of Gastric Pain Symptoms domain, Stomach Heaviness Symptoms domain and /or Diarrhea Symptoms domain, as assessed by the Izumo Scale with electronic device over the 2 consecutive weeks before baseline (assessed on Day 1), and histologic evidence of EGE with  $\geq 30$  eos/hpf in at least 5 hpf in the stomach and/or  $\geq 30$  eos/hpf in at least 3 hpf in the duodenum. Both assessments will be conducted while on stable background therapy. Peak gastric/duodenum eos count will be confirmed by the central reader.

Subjects weighing  $\geq 30$  kg will be enrolled in this study. Currently, there is no administration experience of CC-93538 360 mg once weekly in subjects weighing  $< 40$  kg. Careful and close safety monitoring (eg, for hypersensitivity reaction) should be considered for this population. For subjects weighing  $\geq 30$  kg and  $< 40$  kg, the first 3 weekly SC doses will be administered in the

clinic, with confirmation of concomitant medications and AEs, and those subjects will remain in the clinic for at least 1 hour following dosing for observation, and be monitored every 2 weeks by the site staff by telephone (but not limited to telephone) between regularly scheduled visits until Week 16 (ie, Week 6 [Day 43 ± 3 days], Week 10 [Day 71 ± 3 days], and Week 14 [Day 99 ± 3 days]).

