## **7.3 Method of Treatment Assignment**

### **7.3.1 The Induction Phase and the Maintenance Phase**

Subjects enrolled in the Induction Phase will be centrally randomized on Day 1 after all screening and baseline assessments have been completed and the investigator has verified that the subject is eligible per the inclusion ([Section 4.2](#)) and exclusion criteria ([Section 4.3](#)). Subjects will be randomized 2:1 to receive active CC-93538 treatment (360 mg SC weekly for 16 weeks) or matching placebo for 16 weeks. Treatment assignment at baseline will be stratified by (with/without) concomitant use of corticosteroid treatment at baseline (up to 10 mg/day as the equivalent of prednisone) to ensure an equal balance in the treatment arms. Randomization will be performed through the Interactive Web Response System (IWRS) system.

Subjects enrolled in the Maintenance Phase will be centrally re-randomized on Week 16 (the completion of Induction Phase). Subjects who randomized to receive CC-93538 360 mg SC once weekly in the Induction Phase will be re-randomized 1:1 to receive active CC-93538 treatment (360 mg SC once weekly or 360 mg SC once every other week), and subjects who randomized to receive matching placebo in the Induction Phase will continue placebo. Re-randomization will also be performed through the IWRS system.

Treatment groups are described in [Section 7.2](#). The treatment each subject will receive will not be disclosed to the investigator, study center personnel, subject, Sponsor, or their representatives. The treatment codes will be held according to the IWRS. Further instructions will be provided in a separate IWRS manual.

The study blind should be maintained for persons responsible for the ongoing conduct of the study (after all subjects have completed the Week 48 assessments for endpoint analysis). Blinded persons may include but are not limited to: Clinical Research Physician (also referred to as Clinical Trial Physician), Clinical Research Scientist, Clinical Trial Manager, Study Statistician, Data Manager, Programmers, and Clinical Research Associates. For details of the emergency procedure for unblinding of individual subjects, see [Section 11.4](#).

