## **9 STATISTICAL CONSIDERATIONS**

### **9.1 Overview**

This is a Phase 3, multicenter, randomized, double-blind, placebo-controlled induction and maintenance study to assess the efficacy and safety of CC-93538 in adult and adolescent subjects with EGE. The study will incorporate a 16-week Induction Phase followed by a 32-week Maintenance Phase and an OLE Phase. Subjects will be randomized according to the following stratification factor: concomitant steroid use (yes or no). An independent DMC will be used to review the safety data regularly during the course of the study.

A primary database lock will be performed when all randomized subjects in this study have completed Week 48 of the Maintenance Phase or discontinued the study, including all Safety Follow-up Period data available to date. Analyses in the primary clinical study report (CSR) will be based on this database.

Analysis details not explained in the statistical section of the protocol will be provided in the Statistical Analysis Plan (SAP).

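### When the Mantel-Fleiss criterion fails, the binary-endpoint p-value loses the randomisation stratum that its confidence interval keeps; a stratified exact fallback is a cheap improvement, mainly for Week 48

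*Combined protocol and SAP*

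**What the plan says.** Section 7.3.1 fixes the stratum: "Treatment assignment at baseline will be stratified by (with/without) concomitant use of corticosteroid treatment at baseline". Section 9.1 names the same single factor.

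Section 9.6.3.1 (dichotomous variables) plans a CMH test on that stratum and then gives a fallback if the Mantel-Fleiss criterion fails: "the Fisher's exact test will be performed instead of the CMH test". No stratified or exact-CMH version is mentioned, so the ordinary Fisher test on the pooled 2x2 table is the natural reading. That is an inference from silence.

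The interval has no matching fallback. For each dose against placebo it is "the 2-sided 95% stratified Newcombe CI" "for the difference in proportions using the CMH weights will be provided".

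The same section counts missing data, and data after rescue or prohibited medication, as non-response. Under its multiplicity paragraph every secondary p-value is nominal. The summary of changes for Amendment 4 says the Fisher sentence was added to agree with the SAP, and section 9.1 leaves further detail to the SAP. The combined document contains no separate SAP text on this point.

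**The concern.** The two numbers that will sit side by side in the results table, a p-value and an interval for the difference in proportions, would be built differently: one with the stratum and one without. Elsewhere the plan keeps the stratification. The primary ANCOVA adjusts for concomitant steroid use, and the log-rank test is stratified.

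Dropping a stratum that predicts response makes Fisher's test, already conservative in small samples, more conservative still. At stake is how the key secondary composite is read at Weeks 16 and 48: a p-value offered as a measure of strength of association may be weaker than the data warrant, or may not match its interval. Validity is not at stake.

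**Working it through.** **1. Inputs.** Week 16 arms: "randomized 2:1 to receive CC-93538 360 mg SC once weekly (N = approximately 30) or matching placebo (N = approximately 15", section 3.1.2. Week 48 arms: the 30 active subjects are re-randomised 1:1 (section 7.3.1), so about 15 per regimen against 15 placebo, before any loss at entry to Maintenance. The documents give neither a composite response rate nor the share of subjects on steroids. Assumed ranges: placebo 0-20%, active 20-80%, steroid share 20-80%.

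**2. The plan's own figure.** The only sample-size calculation is for the primary endpoint. With difference 70, SD 70, 2:1 allocation and two-sided 0.05, noncentral-t power is 78.5% at 36 subjects and 81.8% at 39. Then 39/0.9 = 43.3, so 44, rounded up to 45 to keep 2:1. The stated 39 and 45 are reproduced. Nothing comparable exists for the composite.

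**3. When the criterion passes.** For stratum k with R_k responders, n_Pk placebo and n_Ak active subjects:

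- expected placebo responders e_k = n_Pk R_k / (n_Pk + n_Ak)
- lower limit L_k = max(0, R_k - n_Ak)
- upper limit U_k = min(R_k, n_Pk)
- pass if min(Σe_k - ΣL_k, ΣU_k - Σe_k) > 5

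Ignoring strata, at 15 v 30: R/3 > 5 needs R ≥ 16, and 15 - R/3 > 5 needs R ≤ 29. The criterion therefore passes with 16-29 responders of 45, and 16/45 = 36%. At 15 v 15: R/2 > 5 needs R ≥ 11, and 15 - R/2 > 5 needs R ≤ 19. It passes with 11-19 of 30, and 11/30 = 37%.

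Expected responders at 5%/40% are 0.75 + 12 = 12.75 at Week 16 (16 needed) and 0.75 + 6 = 6.75 at Week 48 (11 needed). At 5%/60% and Week 16 they are 0.75 + 18 = 18.75, inside the window.

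**4. Probability that the criterion fails** (exact binomial counts in two strata, over steroid shares 20-80%):

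| Placebo/active | Week 16, 15 v 30 | Week 48, 15 v 15 |
|---|---|---|
| 5%/30% | 97-98% | 99% |
| 5%/40% | 79-84% | 96% |
| 5%/50% | 40-47% | 86% |
| 5%/60% | 10-13% | 65% |
| 5%/70% | about 1% | 36% |

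**5. Effect of the fallback under the rule as planned**: CMH if the criterion is met, otherwise the fallback, with probability-ordered two-sided p-values. The stratum effect at Week 16 is placebo 2%/10% and active 25%/55% by stratum.

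| Scenario | Fisher fallback | Stratified exact fallback | Difference |
|---|---|---|---|
| Week 16, stratum effect, strata 15:8 and 15:7 | 72.1% | 69.4% | -2.7 |
| Week 16, stratum effect, strata 15:7 and 15:8 | 71.9% | 72.9% | +1.0 |
| Week 16, stratum effect, random stratum sizes | 72.3% | 72.0% | -0.3 |
| Week 16, 5%/35%, no stratum effect | 61.0% | 60.3% | -0.7 |
| Week 48, 5%/40%, random strata | 53.1% | 56.4% | +3.3 |
| Week 48, stratum effect, first scenario | 51.3% | 54.9% | +3.6 |
| Week 48, stratum effect, second scenario | 45.3% | 60.2% | +14.9 |

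**6. Size.** With no treatment effect and response 10%/50% by stratum, comparing the two exact tests directly, rejection at Week 16 is 1.7% for Fisher and 2.9% for the stratified exact test. At Week 48 (active 7+8, placebo 8+7) it is 0.9% and 2.8%. The largest null size seen for the stratified fallback at Week 48 was 3.3%.

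**7. Visible conflict.** At 15 v 30 with 40% on steroids, the criterion fails and Fisher disagrees with the stratified interval at the 5% level in 0-4.3% of simulated trials.

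**The case against.** **Frequency is not established.** A reader might infer that the fallback is the expected route for the composite at Week 16. The documents do not support that. They give no response rate, and section 9.3 plans for a mean eosinophil reduction near 80%, so a high histologic response rate cannot be ruled out. The claim holds only if the pooled rate is below about one third. This stands.

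**No dependable power gain at Week 16.** Applying both exact tests to every simulated trial can suggest that stratifying recovers a few points. The plan does not do that: it uses CMH whenever the criterion is met. Under the actual rule the gain disappears, and its sign depends on which stratum holds the odd placebo subject. This stands.

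**Nothing formal depends on it.** The p-values are nominal, Fisher's test holds its size, and the interval that carries the effect estimate is unaffected. This stands, and limits the point to a cheap improvement.

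**The fix does not fully align test and interval.** An exact conditional test concerns a common odds ratio; the Newcombe interval concerns a risk difference. This is true, and equally true of the planned CMH test beside that interval. The fix aligns the stratification only.

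**The Week 48 gain depends on the p-value definition.** At 15 v 15 the pooled null distribution is symmetric, so Fisher's probability-ordered and doubled p-values coincide. For the stratified test they differ: with doubled one-sided p-values the Week 48 change is only about -1 to +5 points. The definition must therefore be fixed in advance.

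**The fallback is deliberate and the SAP may say more.** If the SAP already names a stratified exact test, only the protocol wording needs to follow.

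**Conclusion.** The mismatch is real on the text: when the criterion fails, the test drops the sole randomisation factor and the interval keeps it. It is minor.

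At Week 16 failure is the more likely outcome for active rates up to about 45% with 5% placebo, and unlikely at 60% or more. Changing the fallback is worth about -3 to +1 points of power there, which is essentially nothing. At Week 48 failure is more likely than not up to about 60% active with 5% placebo, and the stratified fallback gained about 3 to 15 points in the simulated scenarios, with size still below 5%.

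These figures rest on assumed response rates, steroid shares, stratum effects and stratum layouts. The case for the change is consistency between test and interval, plus a likely benefit at Week 48.

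The point does not extend to the proportion reducing steroids to zero. Table 2 restricts that endpoint to subjects on concomitant treatment, so there is a single stratum and no mismatch.

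**What to change.** In section 9.6.3.1 and the SAP, make the fallback the exact conditional CMH test stratified by concomitant corticosteroid use at baseline, with two-sided p-values by probability ordering. Keep the stratified Newcombe interval. If the sponsor prefers Fisher's test, say that it is unstratified and that p-value and interval will then differ in stratification.

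The cost is one extra line of specification; the stratum is already collected and the test is in standard software. The downside is a possible small loss of Week 16 power, up to about 3 points, in some stratum layouts.

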## **9.7 Safety Analysis**

Safety analysis will be performed for the Induction Phase and by treatment and in total CC-93538 for the Maintenance Phase. The assessment of safety will include AEs, SAEs, AEs leading to discontinuation of study treatment, changes from baseline in laboratory values and vital signs, and incidence and type of laboratory, vital signs, and physical examination abnormalities. Safety data

will be summarized by treatment group using descriptive statistics. Individual data listings will also be provided.

Adverse events will be monitored during the study, and the data will be analyzed with respect to incidence within each treatment group as well as severity and potential relationship of the AEs to IP.

Laboratory assessments will be performed by a central laboratory. All summaries will be based on the standard International System of Units (SI) provided by the central laboratory. Each subject's hematology, blood chemistry, and urinalysis values will be flagged as "low", "normal", or "high" relative to the normal ranges of the central laboratory.

Summary statistics of actual values and changes from baseline in vital signs will be provided by visit.

Overall safety and tolerability will be summarized for each drug presentation (the 360 mg dose of CC-93538 administered by two injections of 1.2 mL each at a concentration of 150 mg/mL CC-93538 or by one injection of 2.0 mL at a concentration of 180 mg/mL CC-93538 administered with the PFS device constituent part or by one injection of 2 mL at a concentration of 180 mg/mL CC-93538 administered with the [REDACTED] device constituent part) utilizing descriptive statistics.

[figure not shown]

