### Maintenance Phase

Subjects who experience a severe EGE flare and/or worsening of EGE symptoms (for 2 consecutive visits [4 weeks apart], described in [Section 6.4.2.10](#)) at the beginning of or during the Maintenance Phase will need to discontinue participation in the Maintenance Phase and may be eligible to enter the OLE Phase at the ET Visit.

If the gastric/duodenal eos count is required to determine the need for emergent rescue therapy during the Maintenance Phase, the results of the gastric/duodenal eos count will be disclosed as long as the investigator requires the result. The subject may also be eligible to enter the OLE Phase.

Subjects experiencing a mild to moderate EGE flare in the Maintenance Phase will continue the study and will be eligible to enter the OLE Phase following the completion of the Week 48 Visit.

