#### **6.4.2.10 *Worsening of EGE Symptoms, EGE Flare, and the EGE Flare Assessment Visit***

Subjects with a worsening of EGE symptoms during the study, either in the Induction Phase, Maintenance Phase, or the OLE Phase will be required to complete the EGE Flare Assessment Visit as shown in the Table of Events ([Table 4](#), [Table 5](#), and [Table 6](#)). Subjects with increased signs and symptoms of EGE are instructed to contact the investigator and/or study staff to determine if an EGE Flare Assessment Visit is warranted.

- Worsening of EGE symptoms is defined as continuous worsening of symptoms for 2 consecutive visits (4 weeks apart) compared to baseline, measured by the weekly Izumo Scale score ( $\geq$  4 weeks of no change from baseline or  $\geq$  4 weeks of worsening from baseline).

An EGE Flare Assessment Visit including safety and efficacy evaluations can occur at any time during the study. An EGD may be required at the EGE Flare Assessment Visit to determine if use of rescue therapy is clinically indicated. Alternatively, if endoscopy is conducted as an intervention during an emergency department visit or hospitalization for a worsening of EGE symptoms or flare, medical record source data including details of the endoscopic procedure should be collected for the EGE Flare Assessment Visit EGD requirement. In addition, all attempts should be made to collect biopsy samples, and these samples should be sent to the central reader for histologic analysis. The results of the centrally read gastric/duodenal eos count will be blinded to investigative sites with the exception of screening during the Induction Phase and the Maintenance Phase. If the results of the gastric/duodenal eos count are required to determine the need for emergent rescue therapy, the results of the gastric/duodenal eos count will be disclosed as long as the investigator requires the result. If the results of the gastric/duodenal eos count will be disclosed in the Induction Phase, the subject is to be discontinued from the study and will not be allowed to enter either the Maintenance Phase or the OLE Phase. (See [Section 3.1.6](#).)

The investigator will confirm if the worsening of EGE symptoms requires rescue therapy and, thus, is deemed a severe EGE flare according to the following protocol definitions.

Any worsening of EGE symptoms during study participation will be documented as an EGE flare.

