### **7.2.2 Maintenance Phase**

Subjects who are randomized to receive CC-93538 360 mg SC once weekly in the Induction Phase will be re-randomized 1:1 to the following treatment arms:

- CC-93538 360 mg SC once weekly for 32 weeks
- CC-93538 360 mg SC once every other week for 32 weeks. During the Maintenance Phase, matching placebo will be administered once every other week on alternate weeks to maintain the blind.

Subjects who are randomized to receive matching placebo in the Induction Phase will continue the following treatment arm:

- Matching placebo SC once weekly for 32 weeks

For the Maintenance Phase, subjects assigned to one of the CC-93538 360 mg arms will be administered two 1.2 mL CC-93538 SC injections once weekly for 32 weeks or once every other week for 32 weeks. Subjects assigned to the CC-93538 360 mg SC once every other week arm will receive a matching placebo SC dose every other week to maintain blinding. Subjects assigned to the placebo arm will receive matching placebo SC doses.

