### IP in [REDACTED] administration

All subjects currently in the study and any new subjects entering the study will start receiving a single injection of the 360 mg/2 mL [REDACTED] once the fifth amendment to the protocol (Protocol Amendment 5) is implemented, informed consent is obtained, and IP is available at the site. For currently enrolled subjects who did not begin the study with the new [REDACTED] presentation, a switch to the new [REDACTED] presentation will occur at the next regularly scheduled study visit. [REDACTED]

In the event the IP [REDACTED] is not available on-site at the time of Protocol Amendment 5 site approval, subjects should continue receiving the single 2.0 mL injection (180 mg/mL) using PFS presentation until the IP [REDACTED] is available.

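### Section 9.7 gives adverse-event incidence without exposure, although time at risk differs by design in Maintenance and between drug presentations

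*Combined protocol and SAP*

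**What the plan says.** Section 9.7 sets the scope: "Safety analysis will be performed for the Induction Phase and by treatment and in total CC-93538 for the Maintenance Phase". For AEs, "the data will be analyzed with respect to incidence within each treatment group as well as severity and potential relationship" to study drug, and safety data "will be summarized by treatment group using descriptive statistics". It then adds that "Overall safety and tolerability will be summarized for each drug presentation", listing three: two 1.2 mL injections at 150 mg/mL by pre-filled syringe, one 2 mL injection at 180 mg/mL by pre-filled syringe, and one 2 mL injection at 180 mg/mL by the newer device (name redacted).

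Four other places determine how long subjects are at risk.

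- Section 7.2.2 plans 32 weeks of Maintenance in each arm, for example "Matching placebo SC once weekly for 32 weeks".
- Section 3.1.6 says that subjects with a severe flare or worsening in Maintenance "will need to discontinue participation in the Maintenance Phase and may be eligible to enter the OLE Phase at the ET Visit". Section 6.4.2.10 defines worsening as "continuous worsening of symptoms for 2 consecutive visits (4 weeks apart) compared to baseline", and its parenthesis also counts four or more weeks without change.
- Section 7.1 uses the 150 mg/mL syringe throughout Induction and Maintenance and allows it in the open-label extension (OLE). The 180 mg/mL presentations appear only in the OLE.
- Sections 7.2.3 and 7.2.4 tie the 180 mg/mL presentations to Amendments 4 and 5 and to site supply. If the newer device has not arrived, "subjects should continue receiving the single 2.0 mL injection (180 mg/mL) using PFS presentation until the IP" is available. Section 3.1.4 leaves the OLE open-ended after two years.

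**The concern.** A percentage of subjects with an AE mixes the hazard with the time over which events could be seen. Where that time is equal by design the mixing does little harm. Here it is unequal in two places.

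In Maintenance, leaving depends on outcome. A subject who worsens stops contributing Maintenance time, and one who enters the OLE does not attend the two Safety Follow-up Visits (Section 3.1.4), so the lost time is not replaced. The flare does not appear in the AE table in its place either: Section 10.1 keeps symptoms of an assessed flare out of AE reporting unless the flare is serious.

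For presentations, time on each is set by phase and by calendar date. A table of percentages by presentation will largely reflect how long each was used.

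The plan already allows for unequal follow-up elsewhere. Section 9.6.3.1 uses Kaplan-Meier estimates with numbers at risk for flare, rescue therapy and steroid withdrawal. Nothing comparable is named for AEs, although safety is listed among the key secondary endpoints. What is at stake is how the tables read; no test or error rate is affected.

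**Working it through.** The plan gives no figure for the safety analysis to reproduce. From the documents: Induction 16 weeks, Maintenance 32 weeks, OLE at least 2 years, and about 30 active and 15 placebo subjects. The 1:1 re-randomisation leaves about 30 / 2 = 15 per Maintenance arm before losses. The documents give no AE rate, exit rate or time on any presentation, so those below are assumptions, shown with ranges.

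**Model.** The same constant hazard h applies in every group and only time at risk t differs. Percentage with an AE = 1 − exp(−h·t).

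**Maintenance.** Assume 40% would have an AE over a full 32 weeks, and that 40% of placebo and 10% of active subjects leave, with exits spread evenly over phase weeks 4 to 32.

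1. h = −ln(1 − 0.40)/32 = 0.01596 per week.
2. Chance of no AE: 0.600 for a completer; for a leaver, (exp(−4h) − exp(−32h))/(28h) = (0.938 − 0.600)/0.447 = 0.757.
3. Placebo: 1 − (0.6 × 0.600 + 0.4 × 0.757) = 33.7%. Active: 1 − (0.9 × 0.600 + 0.1 × 0.757) = 38.4%.
4. Mean weeks in the phase: placebo 0.6 × 32 + 0.4 × 18 = 26.4; active 0.9 × 32 + 0.1 × 18 = 30.6.
5. The difference is 4.7 points and the ratio 1.14, although the hazards are equal. The rate per person-time is the same in both arms, ratio 1.00.

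If all exits fall at phase week 8, the figures are 28.8% and 37.2%, ratio 1.29. Varying full-phase AE incidence over 20–80%, placebo exit over 20–60% and active exit over 10–20% gives ratios from 1.03 to 1.65 and differences from 0.8 to 23.4 points. The largest difference needs 80% incidence, 60% v 10% exit and every exit at phase week 8.

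**Presentations.** Assume 20% with an AE per 16 weeks.

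| Weeks of use | Percentage with an AE |
|---|---|
| 12 | 1 − 0.8^(12/16) = 15.4% |
| 26 | 1 − 0.8^(26/16) = 30.4% |
| 48 (16 + 32, Induction plus Maintenance) | 1 − 0.8^3 = 48.8% |
| 104 (two years of OLE) | 1 − 0.8^(104/16) = 76.6% |

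With 10% to 40% per 16 weeks, use for 12 v 48 weeks gives from 7.6% v 27.1% to 31.8% v 78.4%. The last two rows of the table show why the direction is open: a presentation used for two years of OLE would look worse than one used for 48 weeks.

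**The case against.** The strongest reply has five parts.

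- **The text says incidence, not crude incidence, and Section 9.1 defers further detail to the SAP.** This stands in part. Exposure-adjusted rates are the kind of detail a SAP could hold, but the supplied document contains no separate SAP text on AEs, and Section 9.7 names no person-time denominator.
- **The summaries are descriptive, and the presentations were compared in randomised single-dose Phase 1 studies (Sections 1.2.2.5 and 1.2.2.6).** True, and it limits the weight of the point. The amendment history describes the presentation summary as a description of the safety profile, so a reader should not infer that it was added as a formal comparison. It will still be read across its columns.
- **The Maintenance effect is small.** Largely right. Severe flare or two-visit worsening in Induction bars entry to Maintenance (Section 6.4.2.11), and mild to moderate flares do not end it. The 4.7-point gap is less than one subject in an arm of 15 (1/15 = 6.7 points). A reader might picture a far larger gap, such as placebo averaging 20 weeks against a full 32. That would need 12/14 = 86% of placebo subjects to leave if exits are spread over weeks 4–32 (32 − 14q = 20), or 12/24 = 50% if all leave at week 8 (32 − 24q = 20).
- **Whether flare subjects leave Maintenance is not settled.** Section 8.2 says a subject with a severe flare may carry on in Maintenance with corticosteroid rescue, which conflicts with Section 3.1.6. The sections must be reconciled, and the size of the Maintenance effect depends on the outcome.
- **Person-time rates bring their own assumption.** They suit a roughly constant hazard. For events that cluster early, such as hypersensitivity or injection-site reactions, long exposure dilutes the rate. Nor do they remove confounding of presentation with phase, calendar time and prior exposure. This stands, and it is why the rates should sit beside the percentages and not replace them as the main summary.

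**Conclusion.** The point holds as a reporting gap. Section 9.7 plans AE incidence by arm and a descriptive summary by presentation with no exposure measure, while the design makes time at risk unequal in both. Equal hazards can then give unequal percentages.

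In Maintenance the distortion is probably modest: about 34% v 38% under the assumed 40% v 10% exits spread over the phase and 40% full-phase incidence. It makes active look worse only if placebo subjects leave more often. It vanishes if exit patterns are equal and reverses if active subjects leave more. Across presentations it could be large, but neither size nor direction can be stated from the documents.

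Three stronger readings are not supported:

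- That percentages will make the newer presentations look safer. Time on each is not given, and the OLE may exceed 48 weeks.
- That the 150 mg/mL syringe carries all first exposure and later presentations contain only subjects who tolerated the drug. Section 7.2.4 notes that the OLE includes subjects previously on placebo, and Section 7.2.3 lets entrants start on a 180 mg/mL presentation.
- That the Induction comparison is compromised. It has a fixed 16 weeks, and subjects with a flare may generally stay in it (Section 3.1.6), so its exposure differs mainly through ordinary dropout.

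**What to change.** In Section 9.7, or in the SAP section that implements it, add for Maintenance and for each presentation:

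1. Subject-years of exposure by group.
2. Exposure-adjusted incidence rates (subjects with an event per 100 subject-years) with 95% confidence intervals, beside the crude percentages.
3. A rule assigning each AE to the phase and presentation in use at onset.
4. Separate columns for subjects whose first CC-93538 dose was with a given presentation and for those switched to it from another.
5. A statement that all of this is descriptive.

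The cost is wording and a few extra tables from dosing and AE dates that are already collected. No procedure or hypothesis test changes. The rates will be imprecise with about 15 subjects per Maintenance arm, and the constant-hazard assumption fits early-clustered events poorly, so the percentages stay.
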